We will stop an individual study in the event of a serious adverse event. If 4 or more subjects experience serious adverse events (as described below), the study will be stopped and the events will be discussed with the IRB to determine whether it is appropriate to continue and/or determine appropriate modifications to the protocol to avoid further adverse events. Adverse events will be considered unanticipated problem if it is unexpected, serious, and would have implications for the conduct of the study.

All adverse events will be submitted for review according to current protocols.

Definition of serious adverse event (SAE)

An SAE is classified as any untoward medical occurrence that, at any dose, meets any of the following criteria (a - f):

- a. Results in death
- b. Is life-threatening

The term 'life-threatening' in the definition refers to an event in which the subject was at risk of death at the time of the event, it does not refer to an event which hypothetically might have caused death if it were more severe.

c. Requires inpatient hospitalization or prolongation of existing hospitalization

A hospitalization or prolongation of hospitalization will not be regarded as a serious adverse event if at least one of the following exceptions is met:

- The admission results in a hospital stay of less than 12 hours
- The admission is pre-planned
- The admission is not associated with an adverse event related to the study medication or study procedures as determined by the study safety officer and data safety monitoring board.
- d. Results in persistent or significant disability / incapacity

Disability means a substantial disruption of a person's ability to conduct normal life's functions.

- e. Is a congenital anomaly / birth defect
- f. Is another serious or important medical event as judged by the investigator.

Breach of Confidentiality

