Unanticipated events will be reported to MU IRB, and both serious and non-serious adverse events will be reported to the MU School of Medicine Data and Safety Monitoring Committee. For reporting to the DSMC, adverse events will be categorized and classified according to Common Terminology Criteria for Adverse Events Scale (CTCAE v3.0). Safety reports will be sent to the safety officer. The PI will be responsible for assembling the data and producing these reports, as well as assuring that all parties obtain copies of these reports.

Qualifications and responsibilities of the Safety Officer:

The safety officer for this trial will be [name]-PhD. **[name] is an Assistant Professor in the Division of Cardiology**. In addition to practicing medicine and cardiology, he is a clinician scientist. As Safety Officer, [name] will review eligibility criteria with [name], and be unblinded as to treatment assignment. He will review all reports sent by the study coordinator to determine whether there is any corrective action, trigger of an ad hoc review, or stopping rule violation that should be communicated to the University of Missouri IRB and the Data and Safety Monitoring Committee. In addition, the safety officer may comment on whether the study investigator needs to report any specific out-of-range laboratory data.

MU Data and Safety Monitoring Committee (DSMC):

The DSMC provides education for investigators, research teams, and faculty regarding data and safety monitoring; reviews proposed Data & Safety Monitoring Plans; establishes Data & Safety Monitoring Boards; conducts independent, interim reviews of study safety and progress; and makes recommendations concerning the continuation of studies, including recommendations regarding the modification, suspension, or termination of a study. The data safety monitoring board minutes will summarize the topics discussed and list the recommendations. Minutes will be signed by the board chair. For the current study the DSMC has 3 voting members representing: Endocrinology, Diabetes and Metabolism, Cardiovascular Diseases and Echocardiology, and Biostatistics. Additional members may be consulted ad hoc as needed and would be reflected in the minutes. In addition, among these members and for the purpose of this clinical trial, 2 voting external members have been included: [name] (University of Chicago) and [name] MD (Washington University).

XIII. Multiple Sites

N/A

XIV. References/Appendices

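### Under SAE criterion (c), a relatedness judgement shared by an unblinded officer decides whether a hospitalisation is serious, so the SAE count is understated and could be classified differently by arm

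*Protocol*

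**What the plan says.** Protocol section VIII, under the definition of a serious adverse event:

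- The opening sentence has no causal condition: "An SAE is classified as any untoward medical occurrence that, at any dose, meets any of the following criteria".
- Criterion (c) is: "Requires inpatient hospitalization or prolongation of existing hospitalization".
- Under (c), an admission "will not be regarded as a serious adverse event if at least one of the following exceptions is met". Two exceptions concern short stays (under 12 hours) and pre-planned admissions. The third is: "The admission is not associated with an adverse event related to the study medication or study procedures". That exception is applied "as determined by the study safety officer and data safety monitoring board".

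Protocol section XII, on the safety officer's responsibilities, says this person will review eligibility "and be unblinded as to treatment assignment". The documents do not say whether the board is blinded, and they describe no blinded assessment of relatedness.

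Under Stopping Rules in section VIII, the same definition feeds a rule for the individual subject and a rule for the study, which begins: "If 4 or more subjects experience serious adverse events". Being serious is also one of the conditions for an unanticipated problem.

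Two provisions soften the effect. Section VII has adverse events collected throughout participation, and section XII sends serious and non-serious events alike to the monitoring committee. The SAP covers the primary outcome only and specifies no safety analysis.

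**The concern.** Seriousness and causality are separate attributes of an event. Seriousness describes what happened to the subject. Relatedness is an opinion about why. The opening of the protocol's definition keeps them apart, but the third exception under (c) merges them for hospitalisations, usually a common kind of serious event in an outpatient trial.

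Two things are at stake. First, the SAE count no longer means serious events from any cause. It means serious events under the other criteria, plus admissions that someone attributed to the study. A reader of the results would not know this from the label. Second, a comparison of SAEs between randomised arms is free of selection only if events in both arms pass through the same filter. Here one of the parties applying the filter knows the assignment. The protocol lists dizziness, fatigue, headache and hyperkalaemia as possible effects of amiloride. For placebo it lists only a possible reaction to the gelatin capsule. The same admission could therefore be judged related in one arm and unrelated in the other.

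**Working it through.** **1. Is there a plan figure to reproduce?** No. The documents give no expected admission rate, no expected SAE count and no operating characteristics for the 4-subject rule. Only the denominator can be checked. Table 1 gives 34 + 24 + 24 + 24 = 106 on amiloride and 17 + 12 + 12 + 12 = 53 on placebo, and 106 + 53 = 159, as stated in section VI.

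**2. How the definition treats an admission.**

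| Admission of 12 hours or more, not pre-planned | Label now | Label if seriousness is set by outcome |
|---|---|---|
| Judged related to drug or procedures | SAE | SAE |
| Judged unrelated, but also meets a, b, d, e or f | SAE | SAE |
| Judged unrelated, meets only (c) | Not an SAE; may be recorded as a non-serious adverse event | SAE |

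Only the third row changes. The size of the understatement is the number of admissions in that row.

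**3. How many admissions could be involved?** Assumptions: an annual admission rate of 2%, 5% or 10% (not in the documents), no dropout, and no deduction for pre-planned or short stays.

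Person-time = 159 × 24/52 = 73.4 years (106 × 24/52 = 48.9 on amiloride; 53 × 24/52 = 24.5 on placebo).

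| Assumed rate per year | All | Amiloride | Placebo |
|---|---|---|---|
| 2% | 1.5 | 1.0 | 0.5 |
| 5% | 3.7 | 2.4 | 1.2 |
| 10% | 7.3 | 4.9 | 2.4 |

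(Arms may not add to the total because of rounding.) If a share f is judged related, f times the total is counted under (c). With f = 0.5 in both arms, 7.3 becomes about 3.7 and 1.5 becomes about 0.7. The shortfall therefore needs no difference in judgement between arms.

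**4. When would the arm comparison be distorted?** With the same true risk in both arms, apparent risk ratio = f(amiloride) / f(placebo). Equal shares give 1. Shares of 0.50 and 0.25 give 2; shares of 0.25 and 0.50 give 0.5. These shares are chosen only to show the mechanism. Distortion needs differential judgement, and it could go either way.

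**5. Why the stopping rules should be handled separately.** Suppose every admission counted toward the 4-subject rule and each occurred in a different subject. With Poisson mean m, P(4 or more) = 1 − e^(−m)(1 + m + m²/2 + m³/6). For m = 1.47, 3.67 and 7.34 (the three totals before rounding) this is 6%, 50% and 93%. Removing the exception everywhere could make the study rule fire on background admissions.

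**The case against.** The strongest defence is that the exception is deliberate and useful: it keeps background admissions from triggering a rule set at only 4 subjects. Step 5 of the working supports this, and it stands. It justifies the exception for the trigger, but not for what is recorded and reported as serious.

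A second defence is that the events do not disappear. Non-serious adverse events also reach the monitoring committee, the exception acts only on (c), and (f) lets the investigator classify other important events as serious. This also stands. A reader might infer that nearly all admissions could vanish from the safety record. The documents do not support that. Even for the SAE table alone, it would require that every admission meets only (c) and is judged unrelated. What remains is that an ordinary admission may meet only (c), and that (f) is discretionary.

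Third, a reader might infer from the officer's unblinding that the SAE comparison is biased by arm. The documents do not show this. The decision is shared with a board whose blinding is not stated, and nothing indicates that judgements differ by arm. Only the opportunity is documented.

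Fourth, no SAE comparison by arm is planned, and with so few events none would be precise. That is true, but with so few events moving two or three also changes the table noticeably. The SAP's silence means that no planned analysis restores admissions from all causes.

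Finally, the assumed rates may be generous for a population that excludes diabetes, recent cardiovascular events and active cancer. That is a fair reason to treat 1.5 to 7.3 as a range and not a forecast.

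**Conclusion.** The point holds as a flaw in definition and reporting. For hospitalisations that meet only criterion (c), seriousness depends on a causal judgement made by the board together with an unblinded safety officer. Relative to a definition by outcome, the SAE count is understated by each such admission judged unrelated. These events are reclassified and not necessarily lost. Differential classification by arm is possible, but its size and direction cannot be known from the documents.

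At an assumed 2-10% annual admission rate, with no dropout and before removing pre-planned or short stays, about 1.5 to 7.3 admissions in total would be exposed to this judgement. The number reclassified would be some unknown part of that. The rule's existence and the officer's unblinding rest on the text alone; the size rests on the assumed rate.

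**What to change.** - **Recording and reporting:** remove the relatedness exception from criterion (c). The exceptions for pre-planned and short stays can stay as they are.
- **Relatedness:** keep it as a separate field, assessed without knowledge of arm.
- **Tables:** report all qualifying hospitalisations and all SAEs by arm, with relatedness alongside, from the adverse event records already collected.
- **Stopping rules:** leave the existing determination by the safety officer and board in place solely for the individual and 4-subject rules, and state that it is separate from the reported relatedness field. A new blinded judgement could not feed those rules and leave their scope unchanged. No trigger is altered.
- **Unanticipated problems:** state which label that test uses, since being serious is one of its conditions.

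The cost is protocol wording, a few more SAE forms, a second relatedness judgement kept apart from the first, and a higher reported SAE count. The SAP is dated November 2025 and written in the past tense. If conduct is complete, the work is a retrospective classification of recorded admissions, and the tables by arm are the part that can still be delivered.

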**STATISTICAL ANALYSIS PLAN
UNIVERSITY OF MISSOURI**

Project Title: Estrogen receptor alpha signaling in endothelial cells exacerbates arterial stiffening via upregulation of ENaC in insulin resistant females

IRB Number: 2012990

Version Date: November 13, 2025

Principal Investigator: [name]

Funding Source: **NHLBI**

Clinical Trial Phase: *Phase II*

Clinicaltrials.gov Number: NCT03837626

Study Drug/Study Device: *Amiloride*

Statistical analysis plan – primary outcome

Linear mixed-effects models were used to evaluate changes in continuous outcome variables. Each outcome was analyzed in a separate model using the **lmer** function in the *lme4* package (R Foundation for Statistical Computing). Fixed effects included time, group, and their interaction (time \times group). A random intercept for participant ID was included to account for within-participant correlation from repeated measurements. Models were estimated using restricted maximum likelihood (REML).

Model assumptions were examined and satisfied, including assessment of normality of residuals, homogeneity of variance, multicollinearity, and evaluation for singular fit. Missing data were handled by the default behavior of **lmer()**, which excludes observations containing NA values; no imputation was performed.

Continuous data were visualized using GraphPad Prism (version 10.0) and are presented as mean values with 95% confidence intervals. Because only two groups were compared, no correction for multiple comparisons was applied.

Significance as set as $p \leq 0.05$.

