- Visit #1: Vital signs (blood pressure and heart rate), weight, DEXA, assessment of brachial and popliteal artery flow-mediated dilation (FMD), cfPWV, femoral artery blood flow, and oral glucose tolerance test (OGTT) (amount of blood drawn not exceeding 55 mL). OGTT will be done when glucose beverage is available. Entire visit is expected to take up to 6 hours. Women of childbearing age will undergo a pregnancy test prior to the DEXA scan and excluded if pregnancy is confirmed. Subject is dispensed the bottle of study drug/placebo and instructed how to take them.
- Visit #2 (1 week after starting the medication +6 days/-2 days): Vital signs, safety questionnaire for side effects, and blood draw for safety laboratories (basic metabolic panel). Entire visit is expected to take up to 30 minutes.
- Visit #3 (4 weeks after starting the medication +/- 6 days): Vital signs, safety questionnaire for side effects, and blood draw for safety laboratories (basic metabolic panel). Entire visit is expected to take up to 30 minutes.
- Visit #4 (8 weeks after starting the medication +/- 6 days): Vital signs, safety questionnaire for side effects, and blood draw for safety laboratories (basic metabolic panel). Entire visit is expected to take up to 30 minutes. If the prior safety visit labs have been within the protocol parameters this visit may be completed as a phone call visit to collect safety questionnaire for side effects and any changes in the subject's health.
- Visit #5 (12 weeks after starting the medication +/- 6 days): Vital signs, weight, DEXA, safety questionnaire for side effects, and blood draw for safety laboratories (basic metabolic panel) and general biochemistries. Subject also will have assessment of brachial and popliteal artery FMD and cfPWV. Women of childbearing age will undergo a pregnancy test prior to the DEXA scan and withdrawn from study if pregnancy is confirmed. Subject will be dispensed a new bottle of study drug/placebo. Entire visit is expected to take up to 3 hours.
- Visit #6 (16 weeks after starting the medication +/- 6 days): Vital signs, safety questionnaire for side effects, and blood draw for safety laboratories (basic metabolic panel). Entire visit is expected to take up to 30 minutes. If the prior safety visit labs have been within the protocol parameters this visit may be completed as a phone call visit to collect safety questionnaire for side effects and any changes in the subject's health.

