There may be no benefit to the subjects in this study. These data will aid in the understanding of how epithelial cell sodium channel (ENaC) contributes to the genesis of arterial stiffness in obese and insulin resistant subjects, preferentially in women. From the screening and baseline tests, all subjects will gain health information about themselves. At the end of the study, results collected will be shared with the subject in face-to-face meetings. In summary, the risks of the treatments are minimal, as witnessed by millions of Americans who are treated with similar drugs each year. The health testing offers some risk, which includes the blood draws. It is possible however, that the benefits to the subjects may be substantial, and the new information on characteristics that increase cardiovascular risk in insulin resistance and obese women will benefit society.

X. Compensation

We have completed multiple clinical studies involving human subjects with adherence rates of greater than 95% and subject retention rates of greater than 85%. 8-12 We utilize a validated retention strategy published by Jeffrey et al. 13 that has been successful. With respect to subject compensation, as shown in **Table 2**, subjects will be paid \$30 for screening visit, \$100 for baseline visit, \$50 for week 1, \$100 for week 4, \$75 for weeks 8, 16 and 20, \$150 for week 12 (interim), and \$350 for week 24 (final visit). Any additional unscheduled safety visits will be compensated \$50. Thus, a total compensation of \$1005 will be provided as study events are completed not including any additional visits.

Table 2. Subject compensation

Visit	Compensation
Screening	30
Baseline test	100
Week 1	50
Week 4	100
Week 8, 16 & 20	75
Week 12 Interim visit	150
Week 24 Final test	350
Unscheduled visit	50

XI. Costs

Subjects will not be charged for any procedures that are part of this research study. The costs of the study will be covered by a NHLBI R01 grant.

XII. Data Safety Monitoring Board

Overall framework for safety monitoring and what information will be monitored:

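### Optional precision gain, not an error: if the SAP's two groups are the randomised arms, a common baseline mean for cfPWV would tighten the week-24 contrast, perhaps by almost nothing

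*SAP*

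**What the plan says.** The SAP has one section on the primary outcome. Its fixed-effects statement is "Fixed effects included time, group, and their interaction". On correlation it says: "A random intercept for participant ID was included to account for within-participant correlation from repeated measurements". It lists no baseline covariate, no equality constraint on baseline means and no term for the sex, menopause and age groups of Protocol Table 1. It does not name the outcome or say what the groups are. The nearest indication is "Because only two groups were compared, no correction for multiple comparisons was applied", which fits amiloride against placebo better than Table 1's four strata.

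On missing values, lmer "excludes observations containing NA values; no imputation was performed". On presentation, the sentence about plots says that continuous data "are presented as mean values with 95% confidence intervals". The text is in the past tense ("Model assumptions were examined and satisfied") and dated November 13, 2025.

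Protocol section VI sizes the trial on cfPWV, using the SD of its change in each stratum. Section VII schedules "assessment of brachial and popliteal artery flow-mediated dilation (FMD), cfPWV, femoral artery blood flow" at Visit 1, where study drug is dispensed, and cfPWV again at Visit 5 (week 12) and Visit 8 (week 24). A baseline value is therefore already collected.

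**The concern.** Randomisation makes the expected baseline mean the same in both arms, so any observed baseline difference is chance. A model with time, arm and time × arm estimates a separate baseline mean for each arm and subtracts the whole chance difference from the week-24 difference. When the correlation between visits is below 1, subtracting all of it overcorrects and adds noise. The random intercept describes the correlation between visits. It does not remove this noise while the baseline means stay free.

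What is at stake is precision only. The estimate is unbiased either way, and the SAP's contrast matches the change-based planning in Table 1.

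**Working it through.** **Table 1 reproduced.** With two-sided α 0.05 (sidedness assumed) and 90% power, the two-sample size per arm is n = 2[SD(1.960+1.282)/Δ]². Premenopausal women (Δ 1.0, SD 1.2): 30.26. Each other stratum (Δ 0.5, SD 0.5): 21.01. Table 1 gives 30 and 21, so its SDs of change are used below.

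**Pooled inputs.** Amiloride 34+24+24+24 = 106; placebo 17+12+12+12 = 53; total 159, of whom 51 are premenopausal women and 108 are in the other strata.
- Mean effect, with no placebo change: (51×1.0 + 108×0.5)/159 = 0.66 m/s.
- Within-stratum variance of change: (51×1.44 + 108×0.25)/159 = 0.632, so SD 0.79 m/s.
- h = 1/106 + 1/53 = 0.0283.

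**Two estimators.** Let D₀ and D₂₄ be the arm differences at baseline and week 24, with a common SD σ and constant correlation ρ.
- SAP model, complete data: D₂₄ − D₀, variance 2σ²(1−ρ)h.
- Common baseline mean: D₂₄ − ρD₀, variance σ²(1−ρ²)h.
- Ratio (1+ρ)/2, so the reduction is (1−ρ)/2.

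A three-visit generalised least squares calculation at 106:53 gave ratios of 0.75, 0.85 and 0.95 at ρ = 0.5, 0.7 and 0.9, as the formula predicts. In simulated complete data, the SAP's week-24 coefficient and the difference in mean change were identical. With 15% of week-24 values missing they correlated at 0.98.

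**Size on Table 1 inputs.** Since SDΔ² = 2σ²(1−ρ), the reduction equals SDΔ²/(4σ²). Neither σ nor ρ is in the documents, so σ = 1.0, 1.2 or 1.5 m/s is assumed for every stratum.

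*Scenario 1: Table 1's SDs of change hold in both arms.*
- Formula: 0.632/(4σ²) = 15.8%, 11.0%, 7.0%.
- Two-visit simulation of baseline adjustment with stratum terms: 15%, 10%, 6%.
- Three-visit common-baseline fits by restricted maximum likelihood (REML): ratios 0.848, 0.893, 0.932.
- Implied ρ = 1 − SDΔ²/(2σ²): premenopausal 0.28, 0.50, 0.68; other strata 0.875, 0.913, 0.944.

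*Scenario 2: the premenopausal 1.2 m/s reflects varying response to amiloride, and the placebo SD of change is 0.5.*
- Two-visit simulation: ratios 0.967, 0.980, 0.993.
- Three-visit common-baseline fits: 0.974, 0.988, 0.985. A separate, smaller run gave 0.980, 0.992, 1.004 with Monte Carlo error of about 0.012–0.016, so none of its values is clearly different from 1.

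**Missing data.** Protocol section X cites past "subject retention rates of greater than 85" percent. With 15% of week-24 values missing, the common-baseline ratios were 0.867, 0.925, 0.945 (scenario 1) and 0.977, 0.997, 0.995 (scenario 2).

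**Power.** In scenario 1 the SAP contrast has SE √(0.632×0.0283) = 0.134 m/s, and 0.66/0.134 is about 4.9. Noncentral t power is 99.8%; in scenario 2 it is above 99.9%.

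**Model-based SE, complete data.** Scenario 1: SAP 0.136, common baseline 0.124, 0.128, 0.131 m/s. Scenario 2 at σ = 1.2: SAP 0.112, common baseline 0.108, baseline as a covariate 0.120.

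**The case against.** The strongest reply is that nothing is wrong. A longitudinal model with free baseline means is standard and unbiased here, and no decision or conclusion would change. That stands, and it is why the point is optional.

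The reply also has force on size. The 15% end needs σ = 1.0 m/s and scenario 1, which implies a correlation of only 0.28 in premenopausal women beside 0.875 elsewhere. Protocol section VI speaks of greater variation in the response of premenopausal women, which favours scenario 2, where the gain is close to nil. It attributes that variation to reproductive hormones, so scenario 1 stays open.

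Four stronger readings are tempting and unsupported:
- *The SAP ignores baseline.* It does not; baseline is most likely the first repeated response. The much larger gain of ρ² (49% at ρ = 0.7) applies only against a follow-up-only contrast, which the SAP does not describe.
- *A reported interval for the treatment difference is too wide.* The SAP's 95% intervals belong to displayed means. It promises no interval for the difference.
- *The trial loses power.* On Table 1 inputs the pooled test already exceeds 99%.
- *15% is a ceiling.* It comes from the assumed SDs; at ρ = 0.5 the formula gives 25%.

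Finally, the protocol also uses the word group for the sex, menopause and age strata. If the SAP means those, baseline means have no reason to be equal and the proposal fails.

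**Conclusion.** The point holds as a free, optional improvement in precision. It is conditional on the SAP's group being the randomised arm, its outcome being cfPWV and time being categorical. Under equal variances and constant correlation the variance reduction is (1−ρ)/2. With Table 1's SDs of change and an assumed cross-sectional SD of 1.0 to 1.5 m/s, the pooled reduction is about 6–15% if those SDs apply in both arms and about 0–3% if the premenopausal SD reflects varying drug response. The gain may therefore be near zero. The algebra is secure; the size is not, because it rests on a correlation and an SD that the documents do not give.

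**What to change.** State in the SAP that the outcome is cfPWV and that group means randomised arm, amiloride or placebo. Then fit a model with a common baseline mean across arms. In lmer: add the Table 1 sex/menopause/age group, keep time as a factor, drop the arm main effect, and keep arm × week 12, arm × week 24 and the random intercept. In practice the arm enters through two indicators, amiloride at week 12 and amiloride at week 24, and the second is the week-24 contrast. Report that contrast with its own 95% interval.

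Do not impose the constraint if group is a non-randomised stratum. Baseline as a covariate is not an equal substitute: in scenario 2 at σ = 1.2 its model-based SE (0.120 m/s) exceeds that of the SAP model (0.112).

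The cost is one definition, one further model fit and a few degrees of freedom, with no new data. The SAP's date and past tense suggest that the analysis may be complete. If unblinded results are already known, keep the SAP's model as primary and report the common-baseline model as a labelled sensitivity analysis.

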- Visit #7 (20 weeks after starting the medication +/- 6 days): Vital signs, safety questionnaire for side effects, and blood draw for safety laboratories (basic metabolic panel). Entire visit is expected to take up to 30 minutes. If the prior safety visit labs have been within the protocol parameters this visit may be completed as a phone call visit to collect safety questionnaire for side effects and any changes in the subject's health.

Visit #8 (24 weeks after starting the medication +/- 6 days): Vital signs (blood pressure and heart rate), weight, DEXA, waist circumference, safety questionnaire for side effects, and blood draw for safety laboratories (basic metabolic panel, lipid panel, and hemoglobin and hematocrit). Subject will also have assessment of brachial and popliteal artery FMD, cfPWV, femoral artery blood flow and oral glucose tolerance test (OGTT) (amount of blood drawn for safety labs, other biochemistries and OGTT not to exceed 70 mL). OGTT will be done when glucose beverage (75g) is available in a volume within 50ml of what was used in the baseline visit. These will minimize variability of the measurements related to changes in the volume of liquid ingested. Women of childbearing age will undergo a pregnancy test prior to the DEXA scan and withdrawn from study if pregnancy is confirmed. Entire visit is expected to take up to 6 hours.

Additional Safety Visits/unscheduled visits might be scheduled in cases of down titration of amiloride dose. Vital signs, safety questionnaire for side effects, and blood draw for safety labs (amount not to exceed 15mL). Unscheduled visits may also occur if safety lab specimens are compromised for any reason or questionable accuracy of the result. Safety labs will then be repeated (amount of blood drawn not to exceed 15 mL).

Medication changes and adverse events collected through out subjects' participation.

Special considerations in case of unforeseeable hardships such as public health emergencies or weather-related events.

In the event of subjects not being able to complete study visits for the reasons described above the following remedial steps will be taken:

- Visits #3,4, 6 and 7 can be completed via a phone interview during which the subject will answer the safety questionnaire (no changes in compensation).

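### With a random intercept as the only random effect, the 12-week and 24-week treatment contrasts share one standard error, which can be too small or too large at week 24

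*SAP*

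**What the plan says.** The SAP (Statistical analysis plan – primary outcome) fits a separate lmer model to each outcome. "Fixed effects included time, group, and their interaction", and "A random intercept for participant ID was included to account for within-participant correlation from repeated measurements". No random slope, visit-specific variance, unstructured covariance, robust standard error or sensitivity analysis is named. On estimation: "Models were estimated using restricted maximum likelihood (REML)". On diagnostics: "Model assumptions were examined and satisfied, including assessment of normality of residuals, homogeneity of variance, multicollinearity, and evaluation for singular fit".

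Protocol section VII schedules the vascular measurements as follows:

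- **Visit #1 (baseline):** "assessment of brachial and popliteal artery flow-mediated dilation (FMD), cfPWV, femoral artery blood flow", plus the OGTT.
- **"Visit #5 (12 weeks after starting the medication +/- 6 days)":** "Subject also will have assessment of brachial and popliteal artery FMD and cfPWV". Femoral blood flow and the OGTT are not listed here.
- **"Visit #8 (24 weeks after starting the medication +/- 6 days)":** FMD, cfPWV, femoral blood flow and the OGTT.

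cfPWV and FMD therefore have three scheduled measurements; femoral blood flow and the OGTT have two. The SAP does not say which visits enter the model, whether time is categorical or linear, or which contrast is primary. Table 1 in protocol section VI gives one SD of the cfPWV change per stratum (1.2 m/s in premenopausal women, 0.5 m/s in the other three) and no time point for it.

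**The concern.** A random intercept with one residual variance imposes equal variance at every visit and one common correlation for every pair of visits. Changes over 12 and 24 weeks must then have the same variance. If measurements 24 weeks apart correlate less than those 12 weeks apart, the model understates the uncertainty of the week-24 contrast and overstates that of the week-12 contrast. If change is narrower at week 24, the reverse holds. At stake are the width of the confidence interval and the error rate of any single-visit treatment comparison, including the end-of-treatment one.

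**Working it through.** **The plan's own figure.** The documents give no standard error or error rate for this model. The nearest figure is Table 1. With n per arm = 2(1.960 + 1.282)² × SD²/Δ², an SD of 1.2 and Δ of 1.0 give 30.26, and an SD of 0.5 and Δ of 0.5 give 21.01. These match the stated 30 and 21. The SDs can thus be taken as SDs of change, but not tied to week 12 or week 24.

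**Inputs.** Random-effects structure and REML: SAP. Visits: protocol section VII. Arm sizes: Table 1, 34:17 in premenopausal women and 106:53 summed over the four strata. Test: two-sided at 0.05 (sidedness assumed). The ratio r = Var(Y24−Y0)/Var(Y12−Y0) is not in the documents, so a range is assumed.

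**Step 1: the SE the model uses.** Take complete data and categorical time. For three visits, the squared pairwise differences sum to six times the within-person sample variance. The residual variance σ² therefore satisfies

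2σ² = [Var(Y12−Y0) + Var(Y24−Y0) + Var(Y24−Y12)] / 3,

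and both time-by-group contrasts get SE = √[2σ²(1/nA + 1/nP)]. The correct week-24 SE is √[Var(Y24−Y0)(1/nA + 1/nP)]. A REML fit to simulated three-visit data with spreading change agreed: the two contrasts had identical SEs of 0.0735, while the week-24 change needed 0.0869. With baseline and week 24 only, the random-intercept SE was 0.0869, equal to the direct one.

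**Step 2: week-24 error rate.** Type I error = 2[1 − Φ(1.96 × R)], where R is model SE divided by correct SE.

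- Case A, Var(Y24−Y12) = Var(Y12−Y0): R = √[(2 + r)/(3r)].
- Case B, extra spread is only added noise at week 24, so Var(Y24−Y12) = Var(Y24−Y0): R = √[(1 + 2r)/(3r)].

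| r | R, case A | Error, A | R, case B | Error, B |
|---|---|---|---|---|
| 0.8 | 1.080 | 3.4% | – | – |
| 1.0 | 1.000 | 5.0% | 1.000 | 5.0% |
| 1.3 | 0.920 | 7.1% | 0.961 | 6.0% |
| 1.5 | 0.882 | 8.4% | 0.943 | 6.5% |
| 2.0 | 0.816 | 11.0% | 0.913 | 7.4% |

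In case A the week-12 ratio is √[(2 + r)/3], so the week-12 test falls from 4.0% at r = 1.3 to 2.4% at r = 2.0.

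**Step 3: in m/s.** If Table 1's SD of 1.2 is the SD of 24-week change, the correct SE at 34:17 is 1.2 × √(1/34 + 1/17) = 0.356. Under case A the model reports 0.385 at r = 0.8, 0.328 at r = 1.3 and 0.291 at r = 2.0.

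**Step 4: simulation.** With 20,000 trials per scenario at 106:53 under case A, SD12/SD24 of 1.0, 0.9, 0.8 and 0.707 (r = 1.0, 1.23, 1.56 and 2.0) gave 4.9%, 6.7%, 8.4% and 11.0% for the week-24 contrast. The overall 2-df interaction test gave 4.8%, 5.0%, 5.3% and 6.1%. Giving the week-24 change its own variance kept its error between 4.6% and 5.1%, including at a more extreme ratio of 0.6.

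**Step 5: r alone does not settle the direction.** With independent visits of variance 0.2, 1.0 and 1.2, the pairwise change variances are 1.2 (0–12), 1.4 (0–24) and 2.2 (12–24). Here r = 1.17, but R = √(1.6/1.4) = 1.07, so the week-24 SE is 7% too large.

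**The case against.** The strongest reply is that no error is shown. A reader might infer that the week-24 intervals are too narrow and its type I error exceeds 5%. The documents do not support that: they give no change variance by visit, and r below 1 makes the test conservative. A reader might also take the week-24 difference as the primary contrast, but the SAP names none. The 11.0% figure needs three categorical visits, a single-visit week-24 test, r = 2 and case A together. All of this stands, and it is why the point is conditional and the range two-sided.

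A second reply is that the SAP reports homogeneity of variance as checked and satisfied. This answers part of the point, and nothing in the documents shows the statement to be wrong. But none of the listed checks is described as examining correlation by visit spacing. Suppose within-person deviations follow a first-order serial correlation ρ between adjacent visits. Every visit then has the same variance, yet r = (1 − ρ²)/(1 − ρ) = 1 + ρ. With ρ = 0.3, r is 1.3 and the check passes. Independent measurement error would pull r back towards 1.

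A third reply is that a covariance pooled over everyone would still be wrong on the protocol's own figures: SDs of change of 1.2 and 0.5 imply a variance ratio of 1.44/0.25 = 5.8 between strata. That stands, and the remedy has to allow for it.

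Finally, the SAP is dated November 2025 and written in the past tense, so replacing the model silently would be post hoc. That affects how the change is reported, not whether it is useful.

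**Conclusion.** The point holds as a conditional one. For cfPWV and FMD, if all three visits enter with time as categorical, the specified model forces one SE on both change contrasts. This is exact for complete data. Whether that SE is right at week 24 depends on variances the documents do not give. Over the assumed range r = 0.8 to 2.0, a nominal 5% week-24 test runs at about 3.4% to 11.0% in case A; if the extra spread is only week-24 noise, r = 1.3 to 2.0 gives about 6.0% to 7.4%. The overall 2-df interaction test is much less affected. Femoral blood flow and OGTT outcomes, measured only at baseline and week 24, are not affected. The documents support neither a claim that the week-24 result is anti-conservative nor one that it is safe. Removing the dependence on r is cheap and worth doing.

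**What to change.** 1. State which visits enter each model, that time is categorical, and which time-by-group contrast is primary.
2. For outcomes with three visits, fit an unstructured covariance, for example with the mmrm package and Kenward-Roger or Satterthwaite degrees of freedom. If nlme::gls is used, note that it does not itself supply Kenward-Roger. Name heterogeneous compound symmetry as the fallback if the model does not converge.
3. If strata are analysed together, let the covariance differ between premenopausal women and the other strata, or fit by stratum.
4. Report the SD of change at weeks 12 and 24, so that readers can see r.
5. Report this analysis beside the random-intercept model the SAP describes, and label it as a change.

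Cost: a 3 × 3 unstructured matrix has six parameters instead of two. That is four more for each covariance matrix fitted, which even a single stratum of 36 to 51 participants can support. There is also a second reported analysis. If change variances turn out equal, little is lost.
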